6.5.2 Covariates

All regression models will adjust for:

- level of encephalopathy at randomization and
- center (as a random effect).

The planned number of enrolling centers is 18, and center will be included in the linear component of the model as an additive random effect.

In addition to adjusting for level of encephalopathy and center as a random effect, sensitivity analyses will be completed by selecting baseline covariates that differ across the two treatments. These covariates will be selected from those covariates listed in section 5.3.

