5.3 Baseline Patient Characteristics

Baseline characteristics will be compared across treatment groups. Table 1 in the MockTablesAppendix.docx document lists out maternal and neonatal characteristics that will be summarized in the primary published paper. In addition to the variables indicated in Table 1 of the MockTablesAppendix.docx document, other baseline characteristics may be investigated internally by the Premie Hypothermia Subcommittee. For programming purposes, the following list contains an example list of infant and maternal characteristics that will or may be investigated as well as dataset and variable names needed to locate the characteristics in the clinical database:

- Infant baseline characteristics (*Variable Type, Form, Variable name in clinical database*)
 - Birth year (*Multiple level discrete, PH05: A.1.a, PH5BRTDT*)
 - GA (*Multiple level discrete – at level of weeks, PH05: A.7.a, PH5GESTW*)
 - Sex (*Binary, PH05: A.8, PH5SEX*)
 - Birthweight (grams) (*Continuous, PH05: A.4, PH5BRTWT*)
 - Length (cm) (*Continuous, PH05: A.5, PH5BRTLN*)
 - Head circumference (cm) (*Continuous, PH05: A.6, PH5HCIRC*)
 - Seizures (*Binary, PH02: C.1, PH2SIEZ*)
 - Level of Encephalopathy (*Binary, PH02: G.4, PH2LECEP*)
 - Inborn/outborn status (*Binary, PH05: A.2, PH5OUTBN*)
 - 1-minute Apgar scores (*Continuous, PH05: A.3.a, PH5APG1*)

- 5-minute Apgar scores (*Continuous, PH05: A.3.b, PH5APG5*)
- Received resuscitation at delivery (*Binary, PH05: B.1-B.5, PH5OXYG / PH5BAGM / PH5CHCOM / PH5INTUB / PH5DRUGS. any equal to 'Y'*)
 - Types of resuscitation (*Multiple level discrete or individual binary, use PH05: B.1-B.5, PH5OXYG / PH5BAGM / PH5CHCOM / PH5INTUB / PH5DRUGS.*)
- Received resuscitation at 10 minutes (*Binary, PH05: C.1-C.5, PH5OXY10 / PH5BAG10 / PH5CHE10 / PH5INT10 / PH5DRG10. Any equal to 'Y'*)
 - Types of resuscitation (*Multiple level discrete or individual binary, use PH05: C.1-C.5, PH5OXY10 / PH5BAG10 / PH5CHE10 / PH5INT10 / PH5DRG10.*)

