6.3 Hospital Course Outcomes

Hospital Course outcomes that may be considered in analysis are:

- Proven NEC (*Binary, PH13, G.4, if PH13PNEC = 2 or 3.*)
- Spontaneous Intestinal perforation without proven NEC (SIP) (*Binary, PH13: G.5, PH13GAST, if PH13GAST = ‘Y’*)

⁵ Subcutaneous fat necrosis may occur after 108 hours.

- seizures after beginning of assigned treatment {Clinical Seizures} (Binary, PH13: D.1.b, D.1.c, D.1.d, D.1.e, taken from PH13SZAB, or PH13SZDM, or PH13SZRW, or PH13SZNT equal to 'Y')
- culture-positive bloodstream or infection of other normally sterile site at >3 days (Binary, PH13: E.1, E.2, PH13SEPT or PH13MENG needs to be 'Y')
- persistent pulmonary hypertension (PPHN) after start of intervention period (Binary, PH13: B.2, PH13PPHN)
- metabolic abnormalities after start of intervention period (Binary, PH13: I.1, I.2, I.3, I.4, I.5, I.6, I.7, PH13HYGL = 'Y' or PH13HYRG = 'Y' or PH13HYCA = 'Y' or PH13HYMA = 'Y' or PH13HYKA = 'Y' or PH13HYRK = 'Y' or PH13HYPH = 'Y')
- treatment with vasopressors and/or steroids after start of intervention period (Binary, PH13: C.7, PH13INOV)
- oliguria after start of intervention period (Binary, PH13: F.1, PH13OLIG)
- anuria after start of intervention period (Binary, PH13: F.2, PH13ANUR)
- liver dysfunction after start of intervention period (AST>200 IU and/or ALT>100 IU) (Binary, PH13: G.7, PH13EAST)
- liver dysfunction after start of intervention period (elevated direct bilirubin) (Binary, PH13: G.8, PH13EDBR)
- clinically diagnosed coagulopathy after start of intervention period (Binary, PH13: H.1, PH13DIC)
- days receiving oxygen/mechanical ventilation (Continuous, PH13: B.6, B.7, B.8, based on PH13DVEN and PH13DOXY, and PH13DCPA)
- Ventilation (Binary, if days receiving oxygen/mechanical ventilation > 0 then = yes)
- duration of NICU stay among survivors (Continuous, PH13: R.1, PH13DSDT (date of discharge) minus PH05: A.1.a, PH5BRTDT (birthdate))
- Bowel perforation (multi-level, = 'NEC' if PH13 G4 = 2, = 'NEC with Perforation' if PH13 G4 = 3, = 'SIP if PH13 G5 = 'Y')
- neurological injury by cranial ultrasound within 24 hours of enrollment, identified by local reader (Binary, PH12, see sub-section Analysis of Ultrasound, CT scan, MRI and encephalopathy outcomes under section 6.5.5.)
- Abnormal neurological examination at discharge
- Death prior to discharge

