- a Bayley III motor score >= 85 (*Binary, among survivors, see section 6.1*)
- Head circumference < 10th percentile, among survivors (*Binary, based on PF05 follow-up form question A.3*)
- Weight < 10th percentile, among survivors (*Binary, based on PF05 follow-up form question A.1*)
- Length/height < 10th percentile, among survivors (*Binary, based on PH05 follow-up form questions*)
- each component of severe and moderate disability (among survivors):

- a Bayley III cognitive score < 70 (*Binary, see section 6.1*)
- a Bayley III cognitive score 70 - 84 (*Binary, see section 6.1*)
- a Bayley III cognitive score >= 85 (*Binary, see section 6.1*)
- Gross Motor Functional (GMFCS) Level of 3-5 (*Binary, see section 6.1*)
- blindness (visual acuity < 20/200 in the best eye as determined by an ophthalmologist) (*Binary, see section 6.1*)
- profound hearing loss (*Binary, see section 6.1*)
- a hearing deficit requiring amplification or cochlear implant to understand commands (*Binary, see section 6.1*)
- Seizures since discharge (*Binary, PF04 A.4 = 'Y'*)
- Abnormal neurological examination at discharge
- differences in MRI findings after cessation of cooling/control (*See subsection "Analysis of Ultrasound, CT scan, MRI and encephalopathy outcomes" under section 6.5.5 for more details*).

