6.5.7 Sensitivity Analysis

In addition to adjusting for level of encephalopathy and center as a random effect, sensitivity analyses may be completed, at the discretion of the Preemie Hypothermia subcommittee, by selecting baseline covariates that differ across the two treatments. These covariates will be selected from those covariates listed in section 5.3. This analysis will only be completed for the primary outcome (death or moderate to severe disability at 18-22 months corrected age) and Death. These sensitivity analyses will be based on the FAS population.

In addition to the FAS population-based analysis, exploratory PP analyses may be done using the PP population on the primary or secondary outcomes at the discretion of the Preemie Hypothermia subcommittee, if the FAS analysis of the primary or secondary outcome results in any clinically notable findings.

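### Gestational age is not prespecified as a covariate for NICU stay, nor enrolment seizures for later seizure outcomes, so precision is forgone

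*SAP*

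**What the plan says.** Section 6.5.2 opens with "All regression models will adjust for" and lists two items: "level of encephalopathy at randomization and" center, the latter as a random effect. The binary and count model formulas in 6.5.1 match this: treatment, encephalopathy and a random center intercept.

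Further covariates appear in two places.

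- Sections 6.5.2 and 6.5.7 describe sensitivity analyses that add imbalanced baseline variables from the 5.3 list. Section 6.5.7 restricts them: "This analysis will only be completed for the primary outcome" and death.
- Section 6.5.5 permits secondary analyses to adjust for covariates, in which case only the adjusted analysis is run. It does not say which covariates or how they are chosen.

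The outcomes at issue are in 6.2 and 6.3. They include "duration of NICU stay among survivors", computed as discharge date minus birth date, and "seizures after beginning of assigned treatment {Clinical Seizures", with clinical seizures during the intervention and electrographic seizures listed separately. Section 5.3 records gestational age in weeks (PH5GESTW) and enrolment seizures: "Seizures (*Binary, PH02: C.1, PH2SIEZ". Section 3.3 stratifies randomization by center and degree of encephalopathy only.

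**The concern.** For two kinds of outcome the strongest candidate predictor is likely to be a variable already in the database, and the plan does not commit to using it. NICU stay counts days from birth in infants born at 33, 34 or 35 weeks, so it can be expected to depend on gestational age. Later seizures follow an eligibility assessment at which clinical seizures alone can satisfy the neurologic criterion (5.1). The plan treats both factors as worth examining: 6.5.8 makes gestational age and qualification on seizures alone subgroup variables, but for the primary outcome only.

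Section 3.4 says larger samples were unfeasible and that the aim is to estimate the effect as precisely as possible. A prognostic covariate left out of a model gives some of that precision away. The open permission in 6.5.5 does not remedy this. It fixes nothing in advance, and when it is used the unadjusted result is not produced, so in an unmasked trial (3.1) the choice could follow the data.

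**Working it through.** The SAP gives no figure on this point: no prognostic strength, no prevalence of enrolment seizures and no distribution of NICU stay. The sizes below are therefore ranges under assumptions.

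**Inputs from the SAP.** Planned N is 168 (3.4), taken as 84 per arm. Gestational age is 33-35 weeks (5.1). The reported effects for binary outcomes are standardized relative risk and risk difference (6.5.1).

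**Seizure outcomes.** Let p be the prevalence of enrolment seizures, and r1 and r0 the later seizure risk with and without them. The overall risk is m = p·r1 + (1−p)·r0. Adjustment leaves the within-stratum part of the variance:

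variance ratio = [p·r1(1−r1) + (1−p)·r0(1−r0)] / [m(1−m)]; SE ratio = its square root; equivalent N = 168 / variance ratio.

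| p | r1 / r0 | m | variance ratio | SE ratio | 168 act like |
|---|---|---|---|---|---|
| 30% | 50 / 40% | 0.43 | 0.243/0.2451 = 0.991 | 0.996 | 169 |
| 30% | 60 / 30% | 0.39 | 0.219/0.2379 = 0.921 | 0.959 | 182 |
| 30% | 70 / 30% | 0.42 | 0.210/0.2436 = 0.862 | 0.928 | 195 |
| 40% | 70 / 20% | 0.40 | 0.180/0.2400 = 0.750 | 0.866 | 224 |
| 30% | 80 / 20% | 0.38 | 0.160/0.2356 = 0.679 | 0.824 | 247 |

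The SE reduction forgone is thus about 0-18%. A separate simulation gave 3-14%. It used 1,500 trials per scenario, 168 infants, prevalence 30-50%, later risk 50-70% versus 15-25%, and a logistic model with post-processed risk difference.

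**NICU stay.** Negative binomial models were simulated with and without gestational age under no treatment effect (1,500 trials per scenario, 140 survivors, mean 20 days, shape 2, encephalopathy in both models). For log-mean changes of 0.1, 0.2, 0.3 and 0.4 per SD of gestational age, the adjusted-to-unadjusted SD ratios were 0.998, 0.962, 0.911 and 0.833, a reduction of about 0-17%. A second set gave 2-20% (600 trials per scenario, mean 22 days at 34 weeks, 15-35% change per week, coefficient of variation 0.35-0.7). Together: roughly 0-20%.

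**Bias.** In the first NICU-stay set the unadjusted log ratio averaged 0.004, 0.000, 0.000 and −0.001 across the four scenarios. Omission does not shift the estimate over randomizations.

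**Chance imbalance.** At 40% prevalence the arm difference in enrolment seizures has SD sqrt(2 × 0.4 × 0.6 / 84) = 7.6 points. With risks of 70% and 20%, a one-SD imbalance moves the outcome difference by 0.5 × 7.6 = 3.8 points. The overall risk is also 40%, so the unadjusted SE of the risk difference is the same 7.6 points. The shift is half of one SE, and the SE already includes it: adjusted SE 0.866 × 7.6 ≈ 6.5, and sqrt(6.5² + 3.8²) ≈ 7.5, which is the unadjusted 7.6 up to rounding.

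**Limits.** These calculations omit the center effect and the priors, and the seizure formula omits encephalopathy level. If enrolment seizures track encephalopathy severity, part of the seizure gain is already captured. A Normal(0,1) prior would also pull a strong seizure coefficient toward zero. The top of the seizure range is therefore somewhat optimistic.

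**The case against.** The case against is substantial, and much of it stands.

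- A reader might infer that the models may adjust for nothing else. The SAP does not support that: 6.5.2 lists what every model includes without excluding more, and 6.5.5 allows additions in secondary analyses. What remains is that no such covariate is named.
- A reader might infer that those optional covariates are picked by arm imbalance or by relation to the primary outcome. In 6.5.5 those rules belong to the sensitivity analyses of the primary outcome; for secondary analyses no rule is given.
- A reader might infer that a chance imbalance would be mistaken for a treatment effect. The arithmetic does not support that: such imbalance is part of the sampling variation that the unadjusted interval covers.
- Growth outcomes such as "Head circumference < 10th percentile, among survivors" might seem to call for adjustment for birth size. The simulated gain was only about 0.5-6% (130 survivors), and with no imputation (6.6) an infant lacking the birth measurement would drop out. Respiratory-support days were not calculated. Neither belongs in the main request.
- The outcomes are low in the hierarchy. Sections 6.2 and 6.3 list outcomes that may be considered, and the table shells that settle what is reported are not at hand. Adjusting for the stratification factors alone is a defensible default.

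The last point lowers the priority but does not remove the gain. Where these models are run, the named covariate improves them at almost no cost.

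**Conclusion.** The point holds as a forgone precision gain, not as an error that biases results. The plan does not prespecify gestational age for NICU stay or enrolment seizures for later seizure outcomes. The adjusted sensitivity analyses do not reach these outcomes, and the permission in 6.5.5 is unspecified and may not apply to 6.2 and 6.3. The SE reduction forgone is roughly 0-20% for NICU stay and 0-18% for seizure outcomes. If the covariates are weakly prognostic, or the three-week span of gestational age matters little, the gain is close to zero. For binary outcomes the gain concerns the standardized relative risk and risk difference that the SAP reports, not necessarily the conditional odds ratio.

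**What to change.** State in 6.5.2, before outcome data by arm are examined, that:

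1. the model for duration of NICU stay also includes gestational age in weeks, centered at 34;
2. the models for clinical and electrographic seizure outcomes in 6.2 and 6.3 also include enrolment seizures (PH2SIEZ).

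Keep encephalopathy level and center in both, and use the Normal(0,1) priors that 6.5.3 and 6.5.4 already give for added covariates. Birth size for growth outcomes and gestational age for respiratory-support days may be left optional or omitted.

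The cost is one extra term in a few models. Both variables come from the eligibility assessment, so little or no loss of infants is expected. Section 4.2 does list a missed neurologic examination as a possible deviation, so an occasional missing PH2SIEZ value cannot be excluded.

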6.5.3 Prior Specification (Binary/Ordinal Primary and Secondary Outcomes)

For the intercept and the encephalopathy terms, Normal(mean = 0, sd=1) priors will be used.

For any other covariates added to the model for sensitivity analyses or any exploratory model, a Normal(mean=0, sd=1) prior will be used.

For the random center effect, we will assume a Normal distribution centered at 0, and the standard deviation parameter will be assumed to follow a half-normal hyperprior with mean equal to 0 and standard deviation equal to 1.

For the term representing the log odds ratio of hypothermia treatment, skeptical, neutral, and enthusiastic priors will be used to estimate posterior distributions for odds ratio when analyzing the primary outcome and primary outcome components. For all other outcomes, only a neutral prior will be used. Because the logistic model will estimate the log odds ratio as the treatment parameter, the priors for the treatment effect will be normal priors on the log odds ratio scale. These normal priors for the log odds ratio are defined below so that the resulting priors in the odds ratio scale have specified properties.

On the odds ratio scale, the skeptical prior for odds ratio will be centered on 1.1 and have a 95% credible interval with an approximate range of 0.28 to 4.40. This skeptical prior will be defined by a normal prior on the log odds ratio scale centered at $\log(1.1) = 0.0953$ with standard deviation (SD) of 0.7072, Normal(mean = 0.0953, sd=0.7072).

On the odds ratio scale, the neutral prior for the odds ratio will be centered on 1.0 and have a 95% credible interval with an approximate range of 0.25 to 4.00. This neutral prior will be defined by a

normal prior on the log odds ratio scale centered at 0 with standard deviation (SD) of 0.7072, Normal(mean = 0, sd=0.7072). Similar priors will be used for the regressions involved in proportional odds modeling of secondary ordinal outcomes.

On the odds ratio scale, the enthusiastic prior for the odds ratio will be centered on 0.75 and have a 95% credible interval with an approximate range of 0.19 to 3.00. This enthusiastic prior will be defined by a normal prior on the log odds ratio scale centered at $\log(0.75) = -0.2877$ with standard deviation (SD) of 0.7072, Normal(mean = -0.2877, sd=0.7072).

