4.1 Modeling Processes, Prior Specification, and Reporting Procedures

- For binary outcomes, the protocol specified that a Bayesian log-binomial regression model with random center effect would be fit to estimate the relative risk of hypothermia relative to normothermia. However, since the protocol was written, an increasing emphasis has been placed on including inference on risk differences in clinical trial reports, so a logistic regression model with random center effect will be fit followed by post-processing of individual predicted probabilities of outcome to estimate posteriors of relative risk and risk differences.¹
 - Weakly informative priors will be used during analyses to better understand the effect of hypothermia on outcomes considered in this trial:
 - On the relative risk and risk difference scales of primary outcome and components, the priors for the treatment effect will include a skeptical prior, a neutral prior, and an enthusiastic prior. For all other outcomes, only the neutral prior will be used.
 - For the intercept and the encephalopathy terms, broad neutral priors will be used.
 - For the random center effect, a Normal prior centered at 0 will be used where the standard deviation parameter of this prior will have a half-normal hyperprior with mean equal to 0 and standard deviation equal to 1.
 - Further details about these priors are given in section 6.4.2 and 6.4.3
 - Posterior distributions, posterior means, posterior probabilities of benefit, and 95% credible intervals will be reported for the effect of hypothermia on the outcomes considered.
- For count outcomes such as days or durations, a negative binomial model with random center effect will be fit to estimate relative risk.
 - Weakly informative priors will be used during analyses to better understand the effect of hypothermia on outcomes considered in this trial:
 - On the relative risk scale, the priors for the treatment effect will include a neutral prior.
 - For the intercept and the encephalopathy terms, broad neutral priors will be used.
 - For the random center effect, a Normal prior centered at 0 will be used where the standard deviation parameter of this prior will have a half-normal hyperprior with mean equal to 0 and standard deviation equal to 1.
 - Further details about these priors are given in section 6.4.2 and 6.4.3

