Model parameter estimates will be generated by fitting three MCMC chains. Each chain will involve at least 10,000 burn-in samples and at least 200,000 additional samples, which will be thinned by at least 5. More samples and more thinning will be done if necessary, to produce good sampling of the posterior. The final MCMC chains will have at least 120,000 useable samples to estimate the posterior distributions necessary for making inference about the treatment effects, (relative risk or outcome difference).

For binary outcomes, the outcome for the j^{th} infant from the i^{th} center will have the following form:

$$y_{ij} = \begin{cases} 0 & \text{survival without moderate / severe disability at 18-22 months corrected age} \\ 1 & \text{death or moderate / severe disability at 18-22 months corrected age} \end{cases}$$

The main covariates will have the form:

$$trt_{ij} = \begin{cases} 0 & \text{normothermia} \\ 1 & \text{whole body hypothermia} \end{cases}$$

$$enceph_{ij} = \begin{cases} 0 & \text{mild encephalopathy} \\ 1 & \text{moderate or severe encephalopathy} \end{cases}$$

The logistic model used for analysis of binary outcomes on the relative risk and risk difference scale will have the following form:

$$y_{ij} \sim \text{Bernoulli}[\pi_{ij}], \text{ where}$$

$$\text{logit}[\pi_{ij}] = \alpha_i + \theta_1 \cdot \text{enceph}_{ij} + \theta_2 \cdot \text{trt}_{ij}$$

β_1, β_2 will have priors as specified in Section 6.5.3

α_i will be the random intercepts due to center. Prior specified in Section 6.5.3.

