- Posterior plot of treatment effect
- Posterior median and posterior standard deviation
- 95% credible interval
- For relative risk, posterior probabilities of >0%, >5%, >10%, and >20% decrease in the primary outcome will be calculated
- For risk difference, posterior probabilities of >0%, >1%, >2%, >3%, and >5% decrease in primary outcome will be calculated
- forest plot of the center level effect and 95% credible intervals.

If the FAS analysis of the primary outcome results in any clinically notable findings, then the primary outcome may also be analyzed in an exploratory fashion using the PP population.

Analysis of Secondary Outcomes

With respect to secondary outcomes, analyses will follow the same process as the primary outcome analysis defined above. See MockTablesAppendix.docx for list of selected variables.

Analysis of Safety (AE) and Hospital Outcomes

Safety and hospital outcomes listed in Sections 6.2 and 6.3 will be analyzed using the FAS population and if necessary, the PP population using relative risk models, proportional odds models, or Negative Binomial models, depending on the type of outcome.

With respect to binary safety outcomes, the estimated posterior distribution of relative risk, θ , based on the data and the neutral prior will be used to determine posterior probabilities of harm from the intervention, $\Pr(\theta > 1 | X)$, as well as 95% credible intervals.

For ordinal safety outcomes, the estimated posterior distribution odds ratio for the cumulative logits, ϕ , will be estimated based on the data and the neutral prior. In addition, posterior probabilities of harm, $\Pr(\phi > 1 | X)$, and 95% credible intervals of ϕ will be calculated.

For count type safety outcome, the estimated posterior distribution of the treatment mean rate, ϕ , will be estimated based on the data and the neutral prior. In addition, posterior probabilities of harm, $\Pr(\phi > 1 | X)$, and 95% credible intervals of ϕ will be calculated.

Analysis of Ultrasound, CT scan, MRI and encephalopathy outcomes

Ultrasound, CT scan, MRI, and encephalopathy outcomes will be analyzed using the FAS population. Head ultrasounds, CT scans, and brain MRIs will be summarized by treatment and time (prior to intervention, during intervention, after intervention, any time). Summaries will be created for number of babies with any abnormal findings during time period data recorded, and for total events across all babies during any time period.

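### The Normal(0,1) intercept prior in the binary models falls on the normothermia arm alone and biases Pr(RR>1) for uncommon safety events toward no harm

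*SAP*

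**What the plan says.** SAP 6.5.3 fixes the prior for the logistic models: "For the intercept and the encephalopathy terms, Normal(mean = 0, sd=1) priors will be used". For the same terms, SAP 4.1 says: "For the intercept and the encephalopathy terms, broad neutral priors will be used".

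In 6.5.1 treatment is coded 0 for normothermia and 1 for hypothermia. The encephalopathy term is coded 0 for mild and 1 for moderate or severe. Effect coding appears only in 6.5.8, for the subgroup models with interactions, so the main models keep reference-cell coding. The neutral treatment prior on the log odds ratio is Normal(0, 0.7072). For the random center effect, "the standard deviation parameter will be assumed to follow a half-normal hyperprior with mean equal to 0 and standard deviation equal to 1".

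For binary safety outcomes, 6.5.5 says that the posterior of the relative risk "based on the data and the neutral prior will be used to determine posterior probabilities of harm from the intervention", that is Pr(RR>1 given the data), reported with 95% credible intervals. Short-term safety is the second primary objective in 2.2.1.

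The heading of 6.5.3 names primary and secondary outcomes. It is nevertheless the only place that defines the neutral prior for binary outcomes, and it assigns that prior to all outcomes other than the primary outcome and its components.

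**The concern.** A treatment prior centered on an odds ratio of 1 should leave two identical arms at Pr(RR>1) of about 0.50. That fails if an informative prior sits on the risk of one arm only. Under reference coding the intercept is the control-arm logit. Normal(0,1) pulls that risk toward 50%, and the treatment coefficient turns negative so that the hypothermia arm still fits the data.

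The size of the pull depends on how far the true risk lies from 50%, so the problem concerns uncommon events. Which of the 6.2 events will be uncommon is an assumption, because the SAP states no rates. Events such as thrombosis, ECMO or esophageal perforation within 108 hours may be; glucose disturbances, thrombocytopenia or seizures need not be.

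At stake is the probability of harm reported for a primary objective, with an error toward reassurance. Nothing planned would expose it: the skeptical and enthusiastic priors vary only the treatment term, and 6.5.7 does not vary the intercept prior.

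**Working it through.** **Inputs.** From the SAP: intercept and encephalopathy priors Normal(0,1), neutral treatment prior Normal(0, 0.7072) and half-normal(1) center SD (6.5.3); coding and logit model (6.5.1); 168 infants (3.4); 18 centers (6.5.2). Assumed: 84 per arm, the event counts below, and a common intercept with its own prior plus center deviations. The last is how 6.5.3 reads, although the equation in 6.5.1 shows only the center intercepts.

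**1. The plan's own figure.** exp(±1.96 × 0.7072) = 0.25 to 4.00. The stated interval of the neutral treatment prior is reproduced.

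**2. What the intercept prior implies.** 1/(1 + exp(±1.96)) gives control risks of 12.3% to 87.7%. P(risk < 10%) = Φ(ln(0.10/0.90)) = Φ(-2.197) = 0.014. P(risk < 5%) = Φ(-2.944) = 0.0016.

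With encephalopathy coded as printed, every eligible infant has the value 1, so intercept plus encephalopathy term has SD √(1² + 1²) = 1.41. The range becomes 1/(1 + exp(±1.96 × 1.41)), or 5.9% to 94.1%. With moderate v severe coding, which the stratification in 3.3 implies, the effective SD in the reference cell stays at 1.

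**3. Identical arms.** Two-parameter grid without centers. The posterior of (a, b) is proportional to Bin(x0; 84, expit(a)) × Bin(x1; 84, expit(a+b)) × N(a; 0, s) × N(b; 0, 0.7072). Pr(harm) = Pr(RR>1) = Pr(b>0), since for every infant RR exceeds 1 exactly when b > 0.

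| Events, control v cooled | s = 1 (moderate v severe) | s = 1.41 (as printed) | s = 2.5 | s = 5 | s = 1, treatment ±0.5 |
|---|---|---|---|---|---|
| 0 v 0 | 0.13 | 0.24 | 0.38 | 0.45 | 0.50 |
| 2 v 2 (2.4%) | 0.21 | 0.32 | 0.43 | 0.48 | 0.50 |
| 4 v 4 (4.8%) | 0.26 | 0.36 | 0.45 | 0.49 | 0.50 |
| 8 v 8 (9.5%) | 0.33 | 0.41 | 0.47 | 0.49 | 0.50 |
| 17 v 17 (20%) | 0.41 | 0.45 | 0.49 | 0.50 | 0.50 |
| 25 v 25 (30%) | 0.45 | 0.47 | 0.49 | 0.50 | 0.50 |

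At 2 v 2 with s = 1 the posterior mean risks are 5.0% control and 3.4% cooled, against 2.4% observed in both. The median RR is 0.67, 95% interval 0.24 to 1.73. The intervals at 0 v 0 (0.16 to 1.59) and 4 v 4 (0.31 to 1.77) also include 1.

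**4. More events in the cooled arm.** Pr(harm), with median RR in brackets:

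| Control v cooled | s = 1 | s = 1.41 | s = 5 |
|---|---|---|---|
| 2 v 4 | 0.41 (0.90) | 0.54 (1.05) | 0.69 (1.30) |
| 2 v 6 | 0.61 (1.13) | 0.73 (1.32) | 0.84 (1.62) |
| 4 v 12 | 0.88 (1.52) | 0.92 (1.70) | 0.95 (1.93) |

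**5. Full model.** With 18 centers, the half-normal(1) center SD and 25% severe infants (assumed), moderate v severe coding gives 0.19, 0.25 and 0.32 for 2 v 2, 4 v 4 and 8 v 8. The printed coding gives 0.31 and 0.37 for 2 v 2 and 4 v 4. The reduced grid is a fair guide.

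**6. Primary outcome.** 59 v 59 (59/84 = 70%) with s = 1 gives RR 1.01, 95% interval 0.84 to 1.21, and Pr(RR>1) 0.55. With s = 1.41 the probability is 0.53.

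**The case against.** A reader might infer that the plan makes cooling look protective on every safety event and hides real harm. The documents do not support that.

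- **Event rates.** None are given, and several 6.2 outcomes may be common. By 20% to 30% per arm the bias is small.
- **Coding.** Under the encephalopathy code as printed, the bias is clearly smaller at every count in the tables.
- **Masking.** An excess is mostly attenuated. Control 2 v cooled 6 still gives an RR above 1, and 4 v 12 still gives Pr(harm) 0.88. Reversal appears only at very low counts such as 2 v 4, and there only with an effective SD of 1.
- **Context of the summary.** 6.5.5 asks for 95% intervals, which include 1 in the identical-arm cases, and 6.5.1 asks for raw counts. 6.5.5 sets no decision threshold on Pr(RR>1).
- **Software.** A program that centers predictors before applying the intercept prior would remove the asymmetry. 6.5.1 permits several R packages.

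These points limit reach and severity. They do not remove the defect. PROC MCMC, the preferred software, fits the model as programmed, and the SAP requires no centering. Without it, Pr(RR>1), a summary that the plan chose to report, is off-center for identical arms under either encephalopathy coding.

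**Conclusion.** The point stands as a bias in Pr(RR>1) for uncommon binary events, toward no harm, together with a conflict between the SD of 1 in 6.5.3 and the broad prior described in 4.1. At 5% or less per arm the bias is large: 0.13 to 0.26 instead of 0.50 with moderate v severe coding, and 0.24 to 0.36 as printed. It is moderate near 10% and small at 20% to 30%.

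The result rests on an assumed event rate, 84 infants per arm, and an uncentered, reference-coded intercept. It does not support a claim that harm is generally masked, and it does not touch the primary efficacy result in any practical way. It should be fixed, but it does not endanger the trial's main conclusion. If the encephalopathy code is corrected to moderate v severe and nothing else changes, this bias grows.

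**What to change.** In 6.5.3, choose one of two changes and leave the Normal(0, 0.7072) treatment prior as it is.

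- **Code treatment -0.5/+0.5 in the main binary models, keeping SD 1.** Identical arms then give exactly 0.50, and control 2 v cooled 4 gives 0.69. The absolute risks are still pulled upward, but equally in both arms (4.3% in each at 2 v 2).
- **Or widen the intercept prior to SD 5.** This leaves 0.45 at 0 v 0 and 0.48 or more at the other counts tabulated. SD 2.5 removes most of the bias, but still gives 0.38 at 0 v 0.

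State that the chosen coding and prior apply whatever software is used, and bring 4.1 into line with 6.5.3.

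The cost is one line of text and a small change in the code. Intervals for rare events become somewhat wider: at 2 v 2 the RR interval moves from 0.24 to 1.73 under the present prior to 0.37 to 2.69 with ±0.5 coding, or 0.32 to 2.98 with SD 5. The primary result hardly moves.
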